8.4. Safety Analysis

All safety assessments, including AEs and SAEs, vital signs measurements, clinical laboratory results, PE results, concomitant medications, and ECG interpretations, will be tabulated and summarized where possible, using descriptive methodology, as needed, by timepoint. Unless otherwise specified, baseline value is defined as the last nonmissing measurement before administration of LOXO-292 in each period. No formal statistical analyses are planned for the safety data. All safety data will be listed by subject.

Concomitant medications will be coded using the World Health Organization (WHO) Drug Dictionary (WHODrug Global B3, 01 March 2019). The incidence of AEs will be presented by severity and by relationship to study drug as determined by the Investigator (see [Appendix 1](#) for AE reporting). All TEAEs will be summarized by system organ class and preferred term, using Medical Dictionary for Regulatory Activities (MedDRA Version 22.0).

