^e Electrocardiograms will be collected after the subject has rested in the supine position for at least 10 minutes, and will be obtained prior to and as close as possible to the scheduled blood draws at Screening and Day -1, Day 1 (before LOXO-292 dosing), Day 2, Day 8 (before ranitidine dosing), Day 12 (before LOXO-292 dosing), Day 13, Day 19 (before omeprazole dosing), Day 23 (before LOXO-292 dosing), Day 24, and EOT (or ET).

^f Vital signs measurements (oral temperature, respiratory rate, and supine blood pressure and heart rate) will be obtained Screening and Day -1, Day 1 (before LOXO-292 dosing), Day 2, Day 8 (before ranitidine dosing), Day 12 (before LOXO-292 dosing), Day 13, Day 19 (before omeprazole dosing), Day 23 (before LOXO-292 dosing), Day 24, and EOT (or ET). Vital signs measurements should be carried out prior to and as close as possible to having blood drawn. Blood pressure and HR will be measured using the same arm for each reading after the subject has been supine for at least 5 minutes.

^g An HDYF? inquiry performed at Screening (after the ICF is signed), at Check-in (Day -1), at each postdose vital signs assessment, and at an appropriate time for all other days.

^h AEs and SAEs will be collected beginning at informed consent. AEs will be recorded throughout the study (ie, from signing of the ICF until EOS, or until ET if the subject discontinues from the study and does not complete a follow-up phone call), either as subject medical history (if the event is reported as beginning prior to signing of the ICF or if the event occurs prior to study drug administration on Day 1 and is assessed as not related to study procedures by the Investigator [or designee]) or as AEs (if the event occurs after signing of the ICF but prior to study drug administration on Day 1 and is assessed by the Investigator [or designee] as related to study procedures, or if the event occurs after study drug administration on Day 1 through EOT or ET regardless of relationship to study drug). From EOT or ET through EOS, only AEs assessed as related to study drug are to be recorded. All SAEs that develop from the time of ICF signing until EOS (or ET if the subject discontinues from the study and does not complete a follow-up phone call) are to be reported.

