ⁱ LOXO-292 will be administered in the morning of Days 1 and 12, following a fast of 10 hours prior to and 4 hours after the LOXO-292 dose. On Day 23, LOXO-292 will be coadministered with omeprazole within 30 minutes of the start of a low-fat meal which will be entirely consumed within 30 minutes.

^j On Day 12, ranitidine will be administered 2 hours (\pm 10 minutes) after the LOXO-292 dose. On Days 8 - 11 and 13 - 18, the morning dose of ranitidine will be administered (with breakfast) approximately 2 hours (\pm 1 hour) after the planned or actual time of the Day 12 LOXO-292 dose and the evening dose of ranitidine will be administered (with a light meal/snack) approximately 10 hours (\pm 1 hour) prior to the planned or actual time of the Day 12 LOXO-292 dose.

^k On Day 23, omeprazole and a single oral dose of 160 mg of LOXO-292 will be coadministered within 30 minutes of the start of a low-fat meal, which will be entirely consumed within 30 minutes. On Days 19-22 and 24-29, omeprazole will be administered following a fast of 2 hours prior to and 1 hour after the omeprazole dose (Note: omeprazole will be administered at approximately the actual time of the Day 12 LOXO-292 dosing).

^l Primary PK blood samples will be collected prior to dosing (within 30 minutes) and 0.25, 0.5, 0.75, 1, 1.5, 2, 2.5, 3, 4, 6, 8, 12, 24, 48, 72, 96, 120, 144, and 168 hours after LOXO-292 administration on Days 1, 12, and 23 for Periods 1, 2, and 3, respectively. The allowed sampling window for PK blood samples will be the following: within 15 minutes prior to dosing for the predose sample timepoint; \pm 5 minutes for sampling timepoints within the first 12 hours; \pm 30 minutes for sampling timepoints > 12 hours < 36 hours; and \pm 60 minutes for the sampling timepoints ranging from 48 to 168 hours.

^m Clinical chemistry panel including CK (fasted at least 8 hours), coagulation parameters, complete blood count, and urinalysis will be performed at Screening, Check-in (Day -1), and Days 2, 7, 11 (before ranitidine dosing), 13, 18 (before ranitidine dosing), 22 (before omeprazole dosing), and 24; and at EOT (Day 30) or ET.

ⁿ Hemoglobin A1c test performed at Screening only.

^o Alcohol breath test and drugs of abuse urine test, including cotinine. Results from the alcohol and drug tests will be used to determine subject eligibility per the inclusion/exclusion criteria.

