7 TREATMENTS

The following is a list of the study treatment sequence abbreviations and ordering that will be used in the baseline TFLs.

Study Treatment labels	Treatment Order on TFLs
Treatment sequence label	
160 mg LOXO-292/ 160 mg LOXO-292 + 150 mg ranitidine BID/ 160 mg LOXO-292 + 40 mg omeprazole QD	
Treatment labels	
160 mg LOXO-292	1
150 mg ranitidine BID	2
160 mg LOXO-292 + 150 mg ranitidine BID	3
40 mg omeprazole QD	4
160 mg LOXO-292 + 40 mg omeprazole QD	5
PK outputs	
160 mg LOXO-292 (fasted)	1
160 mg LOXO-292 (fasted) + 150 mg ranitidine BID	2
160 mg LOXO-292 (fed) + 40 mg omeprazole QD	3

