10.1.1 Definition of Baseline and Change from Baseline

Baseline value is defined as the last non-missing measurement prior to the administration of LOXO-292 in each period, including repeats (vital signs and electrocardiograms [ECGs]) and unscheduled (clinical laboratory parameters) readings (see [Section 10.1.2](#) for definitions of repeat and unscheduled readings). LOXO-292 dosing days are: Day 1 (Period 1), Day 12 (Period 2) and Day 23 (Period 3).

Mean change from baseline is the mean of all individual subjects' change from baseline values. Each individual change from baseline will be calculated by subtracting the individual subject's baseline value from the value at the timepoint. The individual subject's change from baseline

values will be used to calculate the mean change from baseline using a SAS procedure such as Proc Univariate.

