10.4.3 Clinical Laboratory Parameters

Clinical chemistry, hematology and coagulation data will be summarized by parameter and treatment, together with changes from baseline. In addition, all clinical chemistry, hematology, coagulation and urinalysis data outside the clinical reference ranges will be listed by parameter and treatment.

Values for any clinical chemistry, hematology, coagulation and urinalysis values outside the clinical reference ranges will be flagged on the individual subject data listings.

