10.4.5 Electrocardiogram

The ECG data will be obtained directly from the 12-lead ECG tracings. These data include the QT interval calculated using the Fridericia correction (QTcF), the PR, RR and QT intervals, the QRS duration, and heart rate.

Changes from baseline will be calculated. Values for ECG parameters outside the clinical reference ranges will be flagged, including $QTcF > 450$ msec and change from baseline > 30 msec, on the individual subject data listings.

The ECG data will be summarized and listed by treatment, together with changes from baseline.

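### With a pre-LOXO-292 baseline, no scheduled change from baseline can show an effect of ranitidine alone or omeprazole alone; the laboratory change is zero by construction

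*SAP*

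**What the plan says.** **Baseline.** SAP 10.1.1: "Baseline value is defined as the last non-missing measurement prior to the administration of LOXO-292 in each period". It names Days 1, 12 and 23 as the LOXO-292 dosing days, lets an unscheduled laboratory value serve as baseline, and defines change as the value at the timepoint minus baseline. Protocol 8.4 has the same rule but leaves room for exceptions: "Unless otherwise specified, baseline value is defined as the last nonmissing measurement before administration of LOXO-292 in each period".

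**Labels.** SAP 7 lists five treatment labels. Two are for the perpetrator drugs without LOXO-292: "150 mg ranitidine BID" (order 2) and 40 mg omeprazole once daily (order 4).

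**Summaries.** Clinical chemistry, hematology and coagulation data "will be summarized by parameter and treatment, together with changes from baseline" (SAP 10.4.3). SAP 10.4.4 treats vital signs in the same way. SAP 10.4.5 says: "The ECG data will be summarized and listed by treatment, together with changes from baseline". None of these sections makes an exception for the drug-alone labels. SAP 10.4.5 also flags a QTcF change from baseline above 30 msec and an absolute QTcF above 450 msec in the listings.

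**Schedule.** After check-in and before end of treatment, Protocol Appendix 4 (footnote m) places laboratory tests on "Days 2, 7, 11 (before ranitidine dosing), 13, 18 (before ranitidine dosing), 22 (before omeprazole dosing), and 24". None is scheduled on Day 12 or Day 23. ECG and vital signs (footnotes e and f) are taken before the first ranitidine dose on Day 8, before LOXO-292 on Day 12, before the first omeprazole dose on Day 19 and before LOXO-292 on Day 23, among other days.

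**Assignment to treatment.** The SAP gives date windows only for treatment-emergent adverse events (10.4.1). It gives none for laboratory, ECG or vital-sign readings.

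**The concern.** Ranitidine and omeprazole each start four days before the LOXO-292 dose of their period. A baseline taken just before LOXO-292 is therefore taken on the co-administered drug. That suits the LOXO-292 labels, but the drug-alone labels are left without a reference value from before their own drug. A printed mean change of 0 for laboratory tests on ranitidine alone would look like evidence of no effect, when it is only a value subtracted from itself.

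The combination labels do not recover the information, because their baseline already contains any shift caused by the co-administered drug. Such a shift would then be shown correctly in no change-from-baseline column. The point has some relevance for QTcF: Protocol 1.2 lists possible QTc prolongation among the theoretical risks of LOXO-292, and a reader may want to separate what was present before LOXO-292 from what followed it.

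**Working it through.** The documents give no figure on this point, so the check maps the schedule to the baseline rule.

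**Step 1: baseline days** (last scheduled value before LOXO-292 on Days 1, 12 and 23)
- Laboratory: Day -1, Day 11, Day 22.
- ECG and vital signs: Days 1, 12 and 23, all predose.

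**Step 2: laboratory**
- The only scheduled draw on ranitidine alone is Day 11. Change = Day 11 - Day 11 = 0.
- The only scheduled draw on omeprazole alone is Day 22. Change = Day 22 - Day 22 = 0.
- The result is the same whether readings are assigned by study period or by the adverse-event windows.
- An unscheduled draw between Day 11 and the Day 12 dose, or between Day 22 and the Day 23 dose, would replace the baseline. The change could then be non-zero, but it would compare two on-drug values and so would still not be a drug effect.

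**Step 3: ECG and vital signs, two ways of assigning readings**

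| Reading | Assigned by study period | Assigned by the adverse-event windows |
|---|---|---|
| Day 8 predose | ranitidine alone: Day 8 - Day 12 | LOXO-292 alone: Day 8 - Day 1 |
| Day 12 predose | own baseline: 0 | in no window; own baseline: 0 |
| Day 19 predose | omeprazole alone: Day 19 - Day 23 | LOXO-292 + ranitidine: Day 19 - Day 12 |
| Day 23 predose | own baseline: 0 | in no window; own baseline: 0 |

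Under the right-hand column, the drug-alone labels hold no reading, or only a baseline with change 0.

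**Step 4: sign, with assumed effects** (for illustration only: starting level 100, ranitidine +5, omeprazole -4). Day 8 = 100, Day 12 = 105, Day 19 = 105 (ranitidine effect taken as still present), Day 23 = 96.
- By period, Day 8 - Day 12 = 100 - 105 = -5, the reverse of the ranitidine effect.
- By period, Day 19 - Day 23 = 105 - 96 = +9, the reverse of omeprazole minus ranitidine: -(-4 - 5) = +9.
- By adverse-event windows, neither number arises.

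**Step 5: QTcF change flag.** Assume a 35 msec rise from Day 8 to Day 12. By period, Day 8 shows -35 and Day 12 shows 0. By adverse-event windows, Day 12 shows 0 and Day 8 is compared with Day 1. No scheduled reading triggers the > 30 msec flag for that rise. The same holds for a rise from Day 19 to Day 23.

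**Step 6: references already collected**
- Ranitidine: laboratory Day 11 - Day 7 = 105 - 100 = +5; ECG and vital signs Day 12 - Day 8 = 105 - 100 = +5. Both return the assumed ranitidine effect.
- Omeprazole: laboratory Day 22 - Day 18 = 96 - 105 = -9; ECG and vital signs Day 23 - Day 19 = 96 - 105 = -9. The assumed omeprazole effect is -4. The difference is the ranitidine state at the reference: the Day 18 draw is on ranitidine, and Day 19 predose is about 10 hours after the last evening dose (Protocol 3.1). These contrasts estimate omeprazole minus ranitidine.

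**The case against.** The strongest reply is that the rule does its intended job. The secondary objective covers LOXO-292 alone and in two combinations, and a pre-LOXO-292 baseline fits that and is specified in the protocol. The drug-alone labels are needed for adverse-event assignment, and nothing in the documents shows that the laboratory, ECG or vital-sign tables will print a change cell for them. That layout is in the table shells, which are not among the documents. Safety is descriptive, out-of-range laboratory values are listed and flagged, adverse events on each drug alone have their own windows, and QTcF above 450 msec is flagged whatever the baseline.

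Most of this stands as a limit on the consequence. It does not remove the point: SAP 7 and 10.4.3 to 10.4.5 read together call for summaries by treatment with change from baseline and exclude no label, and the stated rule then gives a laboratory change of zero.

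A reader might go further and infer that the ECG and vital-sign columns will print sign-reversed effects. The documents do not support that. It requires the Day 8 and Day 19 predose readings, taken before the first dose of the drug concerned, to be filed under that drug's label. The SAP does not say so. Its only window rule, for adverse events, places predose Day 8 under LOXO-292 alone and predose Day 19 under LOXO-292 plus ranitidine. A reader might also take Day 18 or 19 as a clean omeprazole reference; Step 6 shows that it is not.

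**Conclusion.** The point holds for laboratory data: for two of the five safety labels, the scheduled change from baseline is 0 in every subject and parameter, by construction. This assumes that samples are taken as scheduled and that no unscheduled draw replaces the baseline.

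For ECG and vital signs, the conclusion is that the drug-alone change is uninformative. It is zero or empty if the adverse-event windows are borrowed, and sign-reversed only if Day 8 and Day 19 are filed under the drug-alone labels. The SAP leaves this open, so sign reversal is a possibility and not an established result. Under neither assignment can the > 30 msec flag detect a QTcF rise on ranitidine or omeprazole alone at a scheduled reading.

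The consequence is modest. The primary PK analysis is untouched, and the pre-LOXO-292 baseline remains suitable for the three LOXO-292 labels. The change is worth making before database lock, by which time the SAP must be final, because it replaces an artefactual zero with an interpretable value or removes it.

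**What to change.** In SAP 10.1.1, keep the pre-LOXO-292 baseline for the three LOXO-292 labels and add:

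- **Ranitidine alone.** Baseline is the last value before the first ranitidine dose (Day 7 laboratory; Day 8 predose ECG and vital signs). Compare it with Day 11 laboratory and Day 12 predose ECG and vital signs.
- **Omeprazole alone.** Either omit change from baseline, or report Day 22 minus Day 18 laboratory and Day 23 minus Day 19 predose ECG and vital signs, labelled as a switch from ranitidine to omeprazole and not as an omeprazole effect.
- **Assignment.** Place the Day 8 and Day 19 predose ECG and vital signs under the preceding LOXO-292 treatment with that period's baseline, in line with the adverse-event windows.

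The opening words of the protocol's baseline rule allow these exceptions without a protocol change, and all the readings are already scheduled. The cost is a short SAP paragraph, one extra baseline derivation, and a footnote on the dual role of the Day 8 and Day 19 readings (likewise Day 7 and Day 18 laboratory values where used) and on the ranitidine carry-in. The new contrasts are uncontrolled before-after differences and should stay descriptive.

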10.1.2 Repeat and Unscheduled Readings

Repeat readings occur when the original vital signs or ECG result requires confirmation. Repeat readings are labelled as 'Repeat' in the listings and replace the original readings in all summaries and changes from baseline presentations and calculations. Prior to dosing, all readings taken in addition to the original reading are defined as predose repeats. Postdose repeat readings are defined as readings collected within 15 minutes of the actual time of the original reading.

With the exception of predose results described above, unscheduled readings for vital signs or ECGs are defined as readings collected >15 minutes from the actual time of the original reading. Unscheduled readings are labelled as 'Unscheduled' in the listings. Because unscheduled readings are not associated with any scheduled timepoint, they are excluded from all summaries (with the exception that they may be used as baseline, as stated in [Section 10.1.1](#)).

10.2 Demographics and Subject Disposition

The demographic variables age, sex, race, ethnicity, body weight, height, and body mass index will be summarized and listed. Subject disposition will be summarized and listed.

10.3 Pharmacokinetic Assessment

10.3.1 Pharmacokinetic Analysis

The following PK parameters will be determined where possible from the plasma concentrations of LOXO-292 using non-compartmental methods performed using Phoenix WinNonlin (Certara USA, Inc.) version 8.1 or higher:

Parameter	Definition
AUC _{0-t}	Area under the concentration-time curve from time 0 to the time of last quantifiable concentration (T_{last}) ^a
AUC _{0-∞}	Area under the concentration-time curve from time 0 extrapolated to infinity ^a
%AUC _{extrap}	Percentage of AUC that is due to extrapolation from the last measurable concentration to infinity
C _{max}	Maximum observed concentration
t _{max}	Time of maximum observed concentration
λ _z	Apparent terminal elimination rate constant, where λ _z is the magnitude of the slope of the linear regression of the log concentration versus time profile during the terminal phase
t _{1/2}	Apparent terminal elimination half-life
CL/F	Apparent systemic clearance
V _z /F	Apparent volume of distribution

Note: Additionally, the number of points used to determine λ_z, upper and lower limits of data selection, and coefficient of determination of exponential fit (R²) will be presented in a listing.

^a All AUCs will be calculated using the linear trapezoidal rule for both increasing and decreasing concentrations.

Additional PK parameters may be determined where appropriate.

The PK analysis will, where possible, be carried out using actual postdose times recorded in the raw data. If actual times are missing, nominal times may be used with sponsor approval.

Concentrations are used as supplied by the analytical laboratory for PK analysis. The units of concentration and resulting PK parameters, with amount or concentration in the unit, will be presented as they are received from the analytical laboratory.

C_{max} and t_{max} will be obtained directly from the plasma concentration-time profiles. For multiple peaks, the highest postdose concentration will be reported as C_{max}. In the case that multiple peaks are of equal magnitude, the earliest t_{max} will be reported.

Criteria for handling concentrations below the limit of quantification in Pharmacokinetic analysis

Concentration values that are below the level of quantification (BLQ) will be set to zero, with defined exceptions as follows;

- Any embedded BLQ value (between 2 quantifiable concentrations) and BLQ values following the last quantifiable concentration in a profile will be set to missing for the purposes of PK analysis.
- If there are late positive concentration values following 2 BLQ concentration values in the apparent terminal phase, these values will be evaluated. If these values are considered to be anomalous, they will be set to missing.

- If an entire concentration-time profile is BLQ, the profile will be excluded from the PK analysis.
- If a Period 1 predose concentration is missing, it will be set to 0 (for PK analysis only) by default within the Phoenix WinNonlin software. Handling of missing predose values in Periods 2 and 3 will be assessed on a case by case basis.

Criteria for the Calculation of an Apparent Terminal Elimination Half-Life

Number of Data Points

At least three data points will be included in the regression analysis and preferably should not include C_{max} .

Goodness of Fit

When assessing terminal elimination phases, the R^2 adjusted value will be used as a measure of the goodness of fit of the data points to the determined line.

Regression-based parameters ($AUC_{0-\infty}$, λ_z , $t_{1/2}$, CL/F, and Vz/F) will only be calculated if the R^2 adjusted value of the regression line is greater than or equal to 0.7.

Period of Estimation

The span of time used in determination of the elimination rate constant will be greater than two half-lives, where possible.

Where an elimination half-life is estimated over a time span of less than two half-lives, it will be flagged in the data listings at the discretion of the Pharmacokineticist, and the robustness of the value should be discussed in the study report.

Calculation of AUC

- The minimum requirement for the calculation of AUC will be the inclusion of at least three consecutive plasma concentrations above the lower limit of quantification (LLOQ) with at least one of these concentrations following C_{max} .
- $AUC_{0-\infty}$ values where the percentage extrapolation is less than 20% will be reported. $AUC_{0-\infty}$ values where the percentage extrapolation is between 20 to 30% will be reported, flagged, and included in the descriptive statistics, whilst $AUC_{0-\infty}$ values where the percentage extrapolation is greater than 30% will be reported but excluded from descriptive statistics.

Anomalous Values

If a value is considered to be anomalous due to being inconsistent with the expected PK profile, it may be appropriate to exclude this point from the PK analysis. However, the exclusion of data must have strong justification and will be documented in the raw data and study report.

Embedded BLQ values may be considered anomalous depending on the route of administration and the characteristics of the drug.

Positive predose value(s) greater than 5% of C_{max} may be excluded from the summary statistics of PK tables and statistical analysis at the discretion of the Pharmacokineticist.

